1.2 Experience sampling of Mother-infant interactions (for 7 days)

A computer program has been developed to use personal digital assistants (PDAs, e.g. PalmPilot) to collect experience sampling data from the mother for one week when the baby turns one year of age. The PDA will page the mother three times a day and ask her a series of 10 questions about her most recent interaction with the baby. Questions will ask about their most recent interaction with the baby, about the last time the baby cried and finally, the last time during the day, they were doing something else and the baby wanted their attention. For the evening paging, they will be asked whether they wanted and received social support from their partner and felt understood and cared for by him. Other questions will ask about their positive and negative affect at the end of the day. This procedure has been tried successfully for the past 4 months as part of the Montreal New Mothers Study. Time: 5 minutes per paging.

- **Twelve-month home interview: Second visit (50 minutes)**

Mother

1. Baseline salivary cortisol

Procedures described in the 6 months mother evaluation (See second home visit, section 1).

Infants

1. Questionnaires.

1.1 Health of the baby and breastfeeding questionnaire. Time: 7 minutes.

2. Standardized assessment and experimental tasks

Psychomotor Development. The Bayley Scales of Infant Development (BSID II, Bayley, 1993) are administered at 12 months. The assessment takes 45 minutes.

3. Baseline salivary cortisol

Procedures described in the 6 months infant evaluation (See second home visit, section 4).

- **Eighteen-month home visit (90 minutes)**

Infants

1. Questionnaires.

1.1 Health of the baby questionnaire. Time: 7 minutes.

1.2. Social/Emotional Development.

The Infant-Toddler Social and Emotional Assessment (ITSEA, Briggs-Gowan & Carter, 1998, 18, 24 months) is a parent-report questionnaire, designed as a developmentally and clinically sensitive measure of social-emotional competencies and problems in 1-2 year-olds. It consists of 140 items to evaluate four independent behavioral domains: 1) externalizing, (e.g., high-activity, aggression, defiance, and negative emotional reactivity); 2) internalizing, (e.g., mood regulation problems, social withdrawal and extreme inhibition/shyness); 3) dysregulation (e.g., sleep and eating problems, mood regulation); and 4) maladaptation (e.g., repetitive and stereotypic behaviors). Items are rated on a 3-point scale. Low ITSEA scores are associated with maternal depression and other psychiatric comorbidities (Carter et al, 2001). Low social-emotional competencies are also related to attachment insecurity, poor task mastery and emotion regulation, ineffective coping behaviors (Carter et al, 1999) as well as delayed linguistic development (Irwin et al, 2002). Time to complete: 40 minutes.

2. Behavioral observations

2.1. Mother-Infant Interactions : Home Observation with Q Sort (MBQS 18 months) (Duration ± 45 minutes)

Maternal sensitivity, considered a key quality in establishing secure attachment, is assessed with the Maternal Behaviour Q-set (Pederson et al, 1990). The MBQS yields a single score reflecting the mother's responsiveness to infant signals. Two observers are needed because one distracts the mother while the other observes. This allows observation of the mother under conditions of multiple attentional demands. MBQS scores correlate with other maternal sensitivity ratings and measures of attachment ([name] et al, 1995, 2000, Moran et al, 1992, Pederson et al, 1990). Meta-analysis ([name] et al, 2000b) demonstrated that MBQS scores correlate

with infant attachment security significantly more highly than other observational techniques ($r=.48$ vs $.21$).

- **Eighteen-month laboratory visit (90 minutes)**

Infants

1. Questionnaires

The mother will fill out questionnaires about her child while he/she is undergoing evaluation.

1.1. Temperament.

The Early Childhood Behavior Questionnaire, (Rothbart et al., 200?) is completed at 18 months. Time: 15 minutes.

1.2. Childbearing Attitudes questionnaires (CAQ).

At 18 months, we will use the same 4 subscales of the original questionnaire: maternal worries, maternal self-confidence, identification with pregnancy, and feelings about children (20 items total). Time: 7 minutes.

2. Standardized assessments and experimental tasks

2.1 Attention/impulsivity

2.1.1 The Attention Network Test (ANT, Fan et al., 2002; 18 months)
Assesses executive functions based on latency of response to the direction cued by the middle stimulus in a set. Sets are either congruent (all items point in the same direction) or incongruent (the middle item points in a different direction from the others). Although originally designed for adults, this task has been successfully adapted for children (Swanson et al, 2000; Fan et al, 2002). The current project adapts the standard ANT to study infant attention functions by pairing the middle stimulus with an interesting event (an animated videoclip on one of the lower two monitors) presented subsequently in the location cued by the middle stimulus. In the current study, the cues are sets of five looming fish facing left or right on the central monitor. In congruent sets, all fish face the same side and loom in the same direction. In incongruent sets, the middle fish faces and looms in the opposite direction. The middle fish is a reliable cue to the location of the animation clip, and is also colored more brightly than the others to strengthen the association. During each trial, the cue set is presented for 2 seconds at the top monitor of the triangular array. After a 600-millisecond interval, a 3.5 second animated clip appears in one of the lower two

monitors. The locations where the sets of fish prompt and where the animations appear follow a previously determined random sequence. The training session consists of 10 trials, with all cues congruent, facing left or right in a previously determined random sequence. To facilitate initial pairing between the cue and the location of the animated clip, only the middle fish looms during training; the others are motionless. The test session is a previously determined random sequence of 24 trials in which five fish within the set loom, but only the middle one reliably indicates the location of the subsequent animation clip. The difference between latency to anticipate or respond to the animation clips for congruent and incongruent cues is the measure. Time: 15 min.

2.1.2. Visual Expectation Paradigm, (Haith, Hazan, & Goodman, 1988, 18 months). Time: 15 minutes.

3. Behavioral observations

3.1. Social/Emotional Development.

3.1.1. Attachment (18 months): The *Strange situation* (SS; Ainsworth et al., 1978) is a standard videotaped or filmed laboratory assessment consisting of eight episodes wherein the infant is alone, with mother, with a stranger, or both, in an unfamiliar setting. Episodes are ordered to increase stress in standardized increments that are manageable for the baby. The primary purpose of this paradigm is to assess the establishment and quality of infant-mother attachment, an important early social milestone. Trained coders use standardized coding schemes (Ainsworth et al., 1978; Main & Solomon, 1990) to assign the infant/toddler to one of 4 categories (secure, avoidant, resistant/dependent, disorganized) reflecting the quality of attachment. These categories are differentially associated with later outcomes with the "secure" pattern predicting the most optimal outcomes (e.g., Arend et al, 1979; Renken et al, 1989) and the disorganized pattern having links to later psychopathology (e.g., Carlson, 1998).

In the present study, the *strange situation* serves additional multiple purposes. It 1) is a stressor that reliably elicits a cortisol stress response (e.g., Nachmias et al, 1996; Spangler & Grossmann, 1993; Goldberg et al, in press). For this purpose, it is necessary to administer the *strange situation* in a separate session on its own. Note salivary cortisol samples are taken as described below. 2) allows assessment of social inhibition/impulsivity by coding infant response to the stranger (Greenberg & Marvin, 1982) and 3) allows coding of maternal behaviours known to disrupt formation of attachment (considered markers of risk for child emotional disturbance) using the Atypical Maternal Behavior Instrument for Assessment and Classification (AMBIANCE, Lyons-Ruth & Block, 1996; Lyons-Ruth et al, 1999). The AMBIANCE will also be applied to other videotaped mother-infant interaction sequences. Time: 60 minutes.

3.1.2. Social Inhibition/Impulsivity: As noted above (3.1.1) behaviour to the stranger in the *strange situation* is coded from video.

4. Cortisol Stress reactivity

Saliva samples are collected from infants for cortisol assays at baseline (arrival), and 20 and 40 minutes after the end of the designated stressor. At 18 months, the stressor is the *Strange situation*.

- **Twenty-four month home visit (50 minutes)**

Mother

1. Questionnaires

1.1 Interview

Short version of the questionnaire described in the 6 months mother evaluation (See first home visit, section 1). We will assess the sources of stress in the mother's life, marital quality and health. We expect the interview to take about 45 minutes to complete.

2. Baseline salivary cortisol

Procedures described in the 6 months mother evaluation (See second home visit, section 1).

Infants

1. Questionnaires

1.1. Health of the baby questionnaire. Time: 5 minutes.

2. Baseline salivary cortisol

Procedures described in the 6 months infant evaluation (See second home visit, section 4).

- **Thirty-six month home interview (50 minutes)**

Infants

1. Questionnaires.

1.1 Health of the baby questionnaire. Time: 5 minutes.

2. Standardized assessments and experimental tasks

2.1 Psychomotor Development. The Bayley Scales of Infant Development (BSID II, Bayley, 1993) are administered at 36 months. The assessment takes 45 minutes.

- **Thirty-six month laboratory visit (90 minutes)**

Infants

1. Standardized assessments and experimental tasks

1.1. Attention/Impulsivity.

1.1.1. Snack Delay (Goldsmith & Rothbart, 1996, 36 months): After placing a single Cheerio or M&M under a clear plastic cup, the experimenter instructs the child to wait for the bell to ring before lifting the glass and eating the snack. Four trials follow with timed durations of 10, 20, 30 and 15seconds. Halfway through each timed period, the experimenter lifts but does not ring the bell. Children hear the instructions again following trials 1-3. Score (from film or videotape) is the length of time the child is able to delay before lifting the glass. Time: 5 min.

1.1.2. Whisper Task (Goldsmith & Rothbart, 1996, 36 months) The experimenter instructs the child as follows: 'Let's try to talk very very quietly, just like I am - can you whisper your name to me? OK, let's play this whisper game I know. I have some pictures of some cartoon characters - let's see if you can tell me their names (it's okay if you don't know, it's just for fun). Remember to whisper because that is how you play the game.'" Cards are presented in fixed order, the experimenter asks for a color label or a description of what the character is doing. A reminder to whisper occurs after the first five cards. Scored from film or videotape, based on number of times child speaks above a whisper. Time: 15 min.

1.1.3. Tower Task (Goldsmith & Rothbart, 1996, 36 months). The experimenter explains how to take turns while building a tower out of wooden alphabet blocks. Children are encouraged to keep adding blocks until the tower falls over. Three towers are built. Coded from videotape, based on the number of times the child violates the rule of "turns." Time: 10 min.

2. Behavioral observations

2.1. Social/ Emotional Development.

2.1.1. Attachment (36-months): Reunion behaviour. The *strange situation* was originally designed for 12-18 month-old infants. Adaptations have been developed for 2-5 year-old children based on evidence (Ainsworth et al, 1978) that the key information is obtained in reunion episodes. At this **assessment, mother and infant are separated during the testing period (approximately 1h)**. The mother then returns to the child's testing room and the reunion and free play following it are coded using the scheme for preschool attachment (Cassidy & Marvin, 1987).

2.1.2. Social Inhibition/Impulsivity: As noted above (2.1.1, in the 18-month *Strange situation* section) **behaviour to the stranger in the *strange situation* is coded from video. At 36 months, response to the experimenter is coded using the same coding scheme. In addition, at 36 months, latency to speak to the experimenter and to engage in each task is coded as additional measures of social inhibition.**

3. Cortisol Stress reactivity

Saliva samples are collected from infants for cortisol assays at baseline (arrival), and 20 and 40 minutes after the end of the designated stressor. At 36 months, the stressor is the separation of mother and child during testing.

4. Questionnaire

The mother will fill out the questionnaire about her child while he/she is undergoing evaluation.

4.1. Temperament.

The Early Childhood Behavior Questionnaire (Rothbart et al., 200?) is completed at 36 months. Time: 15 minutes.

IV. Statistical analysis

Power analysis for maternal sensitivity/infant cortisol response.

We hypothesize that decreased maternal sensitivity will be associated with increased cortisol stress responses (obtained with salivary cortisol measures) in infants in the strange situation test at both 18 and 36 months of age. Published work on *infant's* attachment and cortisol stress responses shows strong effects sizes (consistently significant differences despite small sample sizes). However, we propose to address the influence of *mothers'* behaviour on infants' cortisol stress response. Because infants' behaviour may be more strongly related to their own cortisol stress response than would be the mother's behaviour, we reduced expected effect size to the moderate range ($r = .30$; Cohen, 1988). We based our power analysis on two continuous variables (maternal sensitivity and net area under the curve, $\alpha_2 = .008$ and a .80 probability of rejecting H_0 if it is actually false. Under these conditions, we need a sample size of 130 (Cohen, 1988). Assuming that 13% of participant subjects do not complete the study (based on data from a previous project drawing on the same recruitment source and requiring similar levels of commitment), we need 145 mother-infant dyads to assess the influence of maternal sensitivity of infant cortisol stress response. Hence the sample size of 240 subjects should be sufficient.

We identified measures that are indicators of stress and potential mediators and moderators of the effects stress on well-being. Most measures are shortened versions of well -documented and widely used measures in the literature. A few are measures that members of the team have obtained from colleagues who are leading researchers internationally. For example, the reactive responding measure was developed by [name] of UCLA in collaboration with the MacArthur Network on the study of socioeconomic status and health.

The secondary level of analyses will involve a preliminary structural equation modeling, but please note that this is intended as a "value added" approach to the primary analyses described above that are derived from specific hypotheses. Quantitatively, as was noted in the review, we face a challenge, especially concerning the issue of moderating effects vis-a-vis structural equation modeling. We will draw on the expertise of statisticians from the Montreal Prematurity Team.

The analyses will be performed in two stages: first regression and analysis of variance type models and in the second stage structural equation

modeling. Regression analyses and ANOVA analyses will be used to test the stated hypotheses. In particular, tests of interaction effects will be used to assess effect modification (moderating variables). Longitudinal analyses to assess chronicity of effects will be done using multilevel regression models to take into account intra-subject correlation.

In the second stage, structural equation modeling (SEM) will be used to test a structural model expressing the nature and strength of each link between pairs of constructs, integrated in a comprehensive and detailed model that can be statistically tested for fit. In order to identify the “best” model, a sequence of nested comprehensive models will be formulated. Each will be separately analyzed by SEM. The formulation of each model will be based on the conceptual framework presented in the proposal and will be complemented by the results of the statistical analyses of the first stage. Each model is assessed according to well-known statistical criteria pertaining to (1) the overall statistical fit, (2) tests of significance relative to each link, (3) estimation of direct and indirect effects in the network of causal pathways, and (4) the residuals. A comparison of competing models is possible within SEM, provided these models are nested. Hence, among similar (nested) models that are equally meaningful, the most parsimonious can be identified and is considered as “best”. Our hypotheses are essentially based on mediating and moderating variables and causal pathways, rather than simple associations

No standard procedure or formulae are available to estimate sample sizes and power for structural models. Recent simulation studies¹⁴⁰⁻¹⁴¹ indicate that a sample size larger than 200 will reduce the chances of nonconvergence (of the estimation algorithm), of improper solutions (illegal estimations such as a negative variance) and of unacceptable bias of estimators. The size of the available sample will likely range from 210 (all time points and cortisol) to 292 (all time points no cortisol) to 366 (6 month data) to 1 year only (440) and hence will prove sufficient to meet the preceding guidelines. As recommended by Boomsma and Hoogland, newly developed corrective robust statistics will be used to correct the effect of possible nonnormality of our data.

Nevertheless, please note that the primary statistical analyses are designed to test specific hypotheses concerning infant outcome measures that are assessed using laboratory-based measures such as the Rothbart tests for cognitive testing, behavior in the strange situation, salivary cortisol responses to the strange situation as well as basal cortisol levels, etc. In the literature, the sample sizes for studies of such outcomes rarely exceed 10-12 per group and yield significant effects of maternal sensitivity.

V. Continuing Review process

The principal investigator of the present research project along with the research team will continue to read the scientific literature related to the different variables studied in the present protocol. If there are new data showing that some of the protocols used are harmful for participants, or if one of the variables studied has been shown to be related to negative outcomes, the principal investigator will immediately contact the Research Ethics Committee of Douglas Hospital in order to submit these new issues to the committee. Please note there are 15 investigators associated with this project, each of whom is a leading international expert in their field of study. This level of expertise ensures the use of state-of-the-art testing procedures as well as an awareness of emerging ethical issues with their area of research. All procedures are reviewed on a regular basis by an Executive Committee comprised of Drs. [name], [name], [name], [name], [name] and [name]. The Executive meets every 2nd month, while members of the project meet twice annually. The topics of ethics are reviewed at each meeting in order to verify adherence to approved procedures and to up-date protocols where necessary.

VI. Literature

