Participants. Our approach will be to develop a human cohort derived from a study already nearing completion in Montreal (The Montreal Prematurity Study funded by the March of Dimes; PI: [name]). [name] is a collaborator on the MAVAN project, and Drs. [name] and [name] are collaborators on the Prematurity Study. The Prematurity study involves measures of psychosocial stress, nutrition, and family and community living conditions as predictors of gestational length, which is the outcome measure in this project. This project will recruit 5000 women at 13-15 weeks gestation, of which approximately 4000 have been recruited and will have given birth before the start of our project, leaving a population of 1200 potential subjects. Currently, 100 women each month are assessed at 24-26 weeks gestation. There is currently in place an infrastructure for follow-up of women from the Montreal Prematurity Study.

The cohort for the current MAVAN project will be derived from the same population used in the Prematurity Study. In essence the MAVAN Project will serve as a follow-up study derived from the Prematurity Study focusing on a substantially smaller population. The strategy for the MAVAN Project is to take advantage of the multivariate assessment of prenatal adversity in The Montreal Prematurity Study. We will follow infants born at normal weight (controls, n= 120; 3000-3500 g at birth) and low-

birth weight babies exhibiting evidence for intrauterine growth retardation (IUGR, n= 120; 2200-2750 g at birth). These groups are based on the recently published Canadian standards for fetal growth (Kramer, M. S., R. W. Platt, S. W. Wen, K. S. Joseph, A. Allen, M Abrahamowicz, B. Blondel, and G. Bréart. 2001. "A new and improved population-based Canadian reference for birth weight for gestational age." *Pediatrics* 108:), which indicates that the birth weight of 2,750 g represents the 10th percentile, with a weight of 3750 g at the 70th percentile. Our intent is to avoid extreme cases of growth retardation (i.e., < 2,200 g). All babies in this study will be born at > 37 weeks gestation to avoid the complication of prematurity and growth restriction. We will recruit two cases for each case (i.e., two infants of normal birth weight for each infant that is small for gestational age).

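### 2004 plan: three of the four sample sizes used to justify the structural equation models exceed the stated cohort of 240, the cortisol model is not shown to clear the guideline of 200, and 145 dyads do not cover the stated 13% loss

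*Combined protocol and SAP*

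**What the plan says.** All places are in the 2004 combined protocol and SAP.

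- **Cohort size.** III. Methods, Participants: "We will follow infants born at normal weight (controls, n= 120; 3000-3500 g at birth"), with a growth-restricted (IUGR) group also of 120. Section IV repeats the total when it closes the power analysis: "Hence the sample size of 240 subjects should be sufficient".
- **Other recruitment figures in the same Participants text.** It asks for two normal-weight infants per small infant. It expects 126 potential IUGR participants, of whom about 70% (88) would take part, and sets a control target of 252. It also plans to oversample low-SES infants of normal birth weight, without a number.
- **Modeling samples.** IV. Statistical analysis starts its list with the smallest sample, 210, which is for complete data including cortisol. The three larger samples follow: "to 292 (all time points no cortisol) to 366 (6 month data) to 1 year only (440"). The plan concludes that these sizes meet the guideline it cites, where simulation studies "indicate that a sample size larger than 200 will reduce the chances of nonconvergence".
- **Status of the modeling.** "The secondary level of analyses will involve a preliminary structural equation modeling", described as an addition to the primary analyses.
- **Loss allowance.** For the correlation of maternal sensitivity with infant cortisol response, 130 completers are required. "Assuming that 13% of participant subjects do not complete the study", the plan states that "we need 145 mother-infant dyads to assess the influence of maternal sensitivity of infant cortisol stress response".

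**The concern.** An analysis sample is a subset of the enrolled cohort, so it cannot be larger than the cohort. Three of the four modeling samples are larger than the 240 that the same section relies on, and nothing shows where they come from. The reader cannot tell how many children will be enrolled or which cohort the modeling sizes describe.

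The sizes are used to declare the sample adequate. Figures of 292 to 440 suggest a comfortable margin over 200 that a cohort of 240 does not have. The gap matters most for models that include cortisol, where the plan's own figures imply a further large loss.

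The 145 is a separate slip in the same section: it does not deliver the 130 completers at the loss rate that the plan assumes.

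**Working it through.** **1. Modeling samples against 240.** 292/240 = 1.22, 366/240 = 1.53, 440/240 = 1.83. Only 210 is below 240.

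**2. Other enrolment totals that the Participants text supports.** The 13% loss is the plan's.

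| Basis | Total | After 13% loss |
|---|---|---|
| 120 + 120 | 240 | 209 |
| 88 at 2:1 (88 + 176) | 264 | 230 |
| 88 + 252 | 340 | 296 |
| 120 at 2:1 (120 + 240) | 360 | 313 |
| 120 + 252 | 372 | 324 |
| 126 + 252 (every potential IUGR participant joins) | 378 | 329 |

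- **292** is close to 340 × 0.87 = 296.
- **366** fits only 372 (loss 1 − 366/372 = 1.6%) or 378 (loss 1 − 366/378 = 3.2%).
- **440** exceeds every row before any loss: 440/378 = 1.16.
- Going backwards, 292 at 13% loss needs 292/0.87 = 335.6, so 336 enrolled.

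No single row yields all of 292, 366 and 440. The sample also grows from 366 at 6 months to 440 at 1 year. Attrition in one cohort runs the other way. Entry after the 6-month visit could produce a rise, but the plan describes none.

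**3. What a cohort of 240 would leave for the modeling.**

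- All time points, before cortisol loss: 240 × 0.87 = 208.8, about 209.
- Plan's own ratio of samples with and without cortisol: 210/292 = 0.72.
- All time points with cortisol: 208.8 × 0.72 ≈ 150.

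So the non-cortisol model would be just above 200 and the cortisol model well below it. The stated 210 fits a cohort of 240 only with essentially no cortisol loss.

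**4. The correlation sample size.** Inputs from section IV: r = 0.30, two-sided alpha 0.008, power 0.80.

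n = ((z₀.₉₉₆ + z₀.₈₀)/atanh(0.30))² + 3 = ((2.652 + 0.842)/0.3095)² + 3 = 130.4.

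The plan's 130 is reproduced; a bias-corrected version gives 129.5.

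**5. The loss allowance.** 130/(1 − 0.13) = 149.4, so 150 dyads. The stated 145 covers a loss of only 1 − 130/145 = 10.3%. Multiplying by 1.13 instead, which is not the right inflation, gives 147 and so does not explain 145 exactly.

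| Dyads enrolled | Completers at 13% loss | Power (Fisher z) |
|---|---|---|
| 145 | 126 | 78% |
| 150 | 130.5 | 80% |
| 240 | 209 | 96% |

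If the cortisol ratio from step 3 also applied to this test, about 150 pairs would remain from 240, with 86% power.

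**The case against.** The other side has several fair points.

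- **The larger figures are not all without basis.** 292 nearly matches the completers expected from 88 + 252, and 366 is possible under 372 or 378. This stands. A reader might infer that none of the three figures could come from this study, and the documents do not support that. For 292 and 366 the conflict is with the stated 240.
- **A larger cohort may have been intended.** The low-SES oversample has no number, and the pool of potential subjects is 1200. This stands as a limit: 440 exceeds every enrolment total with stated numbers, but a larger intended cohort cannot be excluded. The 1200 is a recruitment source and not a sample.
- **The derivation may sit elsewhere.** The modeling text refers to a framework in a proposal and to numbered references, while the literature list here is unnumbered. It may have been carried over from another application. That would explain the mismatch but would not remove it.
- **The 209 clears the guideline.** A reader might infer that a cohort of 240 just meets the guideline throughout. The 209 is before cortisol loss, so this is unsupported for the cortisol model.
- **Little depends on it.** The modeling is secondary and preliminary, the guideline is soft, and the later 72-month protocol reports about 600 children enrolled. This stands and sets the weight of the point. The later enrolment does not supply a derivation for the 2004 figures.

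**Conclusion.** The point holds, with minor impact. Within the 2004 plan, 292, 366 and 440 (122%, 153% and 183% of 240) contradict the stated cohort. Behind this lies a cohort that is never fixed: 120 + 120, the 2:1 ratio, and 88 with 252 controls give different totals.

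If the cohort is 240, the claim of sufficiency is not supported for models that use cortisol, where about 150 would remain. This rests on two assumptions: that the 13% loss applies to the modeling sample, and that the ratio 210/292 carries over to a cohort of 240. It does not show that the models would fail, because the guideline speaks only of lower chances of trouble.

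The loss allowance is short by 5 dyads, which costs about 2 points of power if only 145 were enrolled. A reader might infer that the correlation test is underpowered. It is not: 240 enrolled gives about 96%, and the plan's conclusion for that test stands.

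**What to change.** - In III. Methods, Participants, state one planned total that reconciles 120 + 120, the 2:1 ratio and 88 + 252, and give a number for the low-SES oversample.
- In section IV, derive the modeling samples from that total and the 13% loss, separately for models with and without cortisol, or delete 292, 366 and 440.
- If the total is 240, say that about 209 would be available for the non-cortisol model, and that the guideline of more than 200 is not shown to be met for the cortisol model.
- Explain or correct the rise from 366 at 6 months to 440 at 1 year.
- Change 145 to 150 and keep the conclusion that 240 suffices for the correlation.

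The cost is wording and a few figures in the Participants and Statistical analysis sections of the 2004 document. Neither the design nor the planned analyses change.
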